4.1.8 Drug accountability

The investigator/ pharmacist/ investigational drug storage manager will receive the investigational drugs delivered by the sponsor when the following requirements are fulfilled:

- approval of the study protocol by the Institutional Review Board (IRB) / ethics committee,
- availability of a signed and dated clinical trial contract between the sponsor and the Head of Trial Centre,
- approval/notification of the regulatory authority, e.g. competent authority,
- availability of the curriculum vitae of the principal investigator,
- availability of a signed and dated clinical trial protocol or immediately imminent signing of the clinical trial protocol,
- availability of the proof of a medical licence for the principal investigator,
- availability of the Form 1572 (only applicable for (United States (US)).

The investigator/ pharmacist/ investigational drug storage manager must maintain records of the product’s delivery to the trial site, the inventory at the site, the use by each patient, and the return to the sponsor or alternative disposition of unused product(s), on the respective forms in the ISF.

These records will include dates, quantities, batch/serial numbers, expiry (‘use by’) dates, and the unique code numbers assigned to the investigational product(s) and trial patients. The

Proprietary confidential information.

© 2018 Boehringer Ingelheim International GmbH or one or more of its affiliated companies. All rights reserved.

This document may not - in full or in part - be passed on, reproduced, published or otherwise used without prior written permission.

investigator / pharmacist / investigational drug storage manager will maintain records that document adequately that the patients were provided the doses specified by the CTP and reconcile all investigational product(s) received from the sponsor. At the time of return to the sponsor or designee, the investigator / pharmacist / investigational drug storage manager must verify that all unused or partially used drug supplies have been returned and that no remaining supplies are in the investigator's possession. Account must be given for any discrepancies.

4.2 CONCOMITANT THERAPY, RESTRICTIONS, AND RESCUE TREATMENT

4.2.1 Rescue medication, emergency procedures, and additional treatment(s)

In principle, any additional concomitant therapy considered necessary for the patient's welfare may be given at the discretion of the investigator. Stable doses of concomitant therapies for chronic conditions, for which neither the condition nor the treatment are judged to exclude the patient from participation (cf. [Section 3.3.3](#)), are permissible. However, all concomitant medications being taken by eligible patients must be carefully evaluated, and questions on the use of concomitant medications should be discussed with the BI clinical monitor.

In the event that a patient experiences an intolerable increase of psoriasis during the course of the trial, topical steroids of US class 6 (mild, such as desonide) or US class 7 (least potent, such as hydrocortisone) will be permitted for use limited to the face, axilla, and/or genitalia. Details of the drug used and the reason must be recorded in the electronic case report forms (eCRF). These topical medications should not be used within approximately 24 hours prior to visits requiring the PASI.

Investigational products are not allowed during the course of the trial.

In case of adverse events in need of treatment, symptomatic therapy according to the judgment of the investigator will be permitted. All concomitant and/or rescue therapies will be recorded on the appropriate pages of the eCRF.

There are no special emergency procedures to be followed.

Patients with a positive IGRA testing (Tb screening) at the roll-over visit should be followed-up according to local guidelines.

4.2.2 Restrictions

4.2.2.1 Restrictions regarding concomitant treatment

The medications (or classes of medication) listed in [Table 4.2.2.1:1](#) must not be taken for the specified times before the roll-over visit and for the whole duration of the study including the Extended Follow-up Period.

Table 4.2.2.1: 1 Restricted medications

Investigational products not otherwise described below (except 1311.2 study drug)	Throughout the duration of preceding trial 1311.2, and for the whole duration of this trial, including any interim period between the trials and the Extended Follow-up Period.
Any biological agents, including but not limited to infliximab, etanercept, adalimumab	Throughout the duration of preceding trial 1311.2, and for the whole duration of this trial, including any interim period between the trials and the Extended Follow-up Period
Oral or injectable psoriasis medications (not biologicals) including but not limited to retinoids, methotrexate, cyclosporine, fumarates, or any other drugs known to possibly benefit psoriasis. Systemic corticosteroids in any dosage form. Any drug known to interfere with or to aggravate psoriasis including but not limited to lithium and interferons, or Phototherapy (UVB, PUVA, UVA).	Throughout the duration of preceding trial 1311.2, and for the whole duration of this trial, including any interim period between the trials and the Extended Follow-up Period
Steroids, retinoids, vitamin D analogs, vitamin A analogs and anthralin in any formulation (i.v., s.c., topicals, oral).	Throughout the duration of preceding trial 1311.2, and for the whole duration of this trial, including any interim period between the trials and the Extended Follow-up Period. (for exceptions cf. Section 4.2.1)

4.2.2.2 Restrictions regarding vaccination

Live vaccinations during the study are not allowed. Bacille Calmette-Guérin vaccines (BCG) are not allowed throughout the duration of preceding trial 1311.2, and for the whole duration of this trial, including any interim period between the trials. It is recommended that patients are advised not to take any live vaccines or BCG vaccines for up to 1 year after the last administration of study drug.

4.2.2.3 Restrictions on diet and life style

Patients must be fasted for at least 8 hours prior to collection of the safety laboratory samples, starting from the initial roll-over visit.

Patients should refrain from excessive physical activity at least 24 hours prior to study visits, during the course of the study (competitive sport etc.).

Use of tanning beds is not allowed during the course of the study.

4.3 TREATMENT COMPLIANCE

Dose administration compliance will be assured by administration of all study medication under supervision of the investigating physician or a designee at the research site. The measured plasma concentrations will provide additional information about compliance.

Proprietary confidential information.

© 2018 Boehringer Ingelheim International GmbH or one or more of its affiliated companies. All rights reserved.
This document may not - in full or in part - be passed on, reproduced, published or otherwise used without prior written permission.

5. VARIABLES AND THEIR ASSESSMENT

5.1 EFFICACY - PHARMACODYNAMICS

5.1.1 Endpoints of efficacy

5.1.1.1 Primary endpoint of efficacy

The primary efficacy endpoint is achievement of a $\geq 90\%$ reduction in PASI score from baseline (i.e., achieving PASI₉₀) at week 48 in the Extended dosing period. Baseline PASI for this study is defined as the baseline PASI for the 1311.2 study.

5.1.1.2 Secondary endpoints of efficacy

The following secondary endpoints will all be evaluated at week 48 in the Extended dosing period:

- achievement of PASI₅₀
- achievement of PASI₇₅
- achievement of PASI₁₀₀
- achievement of sPGA of clear or almost clear

5.1.1.3 Further endpoints of efficacy

Additional efficacy analyses will include, but are not limited to, the following:

- achievement of PASI₅₀ at all Extended dosing period visits where PASI is collected
- achievement of PASI₇₅ at all Extended dosing period visits where PASI is collected
- achievement of PASI₉₀ at all Extended dosing period visits where PASI is collected
- achievement of PASI₁₀₀ at all Extended dosing period visits where PASI is collected
- achievement of sPGA of clear or almost clear at all visits where sPGA is collected
- time to loss of PASI₅₀, which is a time to failure endpoint. This will be repeated using PASI₇₅, PASI₉₀, and PASI₁₀₀ as the endpoint.
- sPGA will be evaluated in terms of time to loss of response which is defined as a score exceeding 1, and will be evaluated as a time to failure endpoint
- change from baseline in Pain-VAS (in subgroup of patients with psoriatic arthritis only where baseline VAS is from 1311.2)
- mean DLQI scores at all Extended dosing period visits where PASI is collected

5.1.2 Assessment of efficacy

The PASI measures the severity of a patient's psoriasis and the percent of the patient's skin that is affected. See [Section 10.1](#) for a detailed description of the PASI.

The Static Physician Global Assessment (sPGA) is a 6 point scale used by physicians to describe the severity of a patient's psoriasis. See [Section 10.2](#) for a detailed description of the sPGA.

Proprietary confidential information.

© 2018 Boehringer Ingelheim International GmbH or one or more of its affiliated companies. All rights reserved.

This document may not - in full or in part - be passed on, reproduced, published or otherwise used without prior written permission.

The Pain-VAS is a Visual Analogue Scale used to assess a patient's psoriatic arthritis. See [Section 10.3](#) for a detailed description of the Pain-VAS.

Immunogenicity testing (Anti-Drug Antibodies (ADA)) will be performed at the visits specified in the [Flow Chart](#) in order to detect the emergence of antibodies.

The Dermatology Life Quality Index (DLQI) is a questionnaire that determines a patient's quality of life. See [Section 10.4](#) for a detailed description of the DLQI.

5.2 SAFETY

5.2.1 Endpoint(s) of safety

5.2.1.1 Primary endpoints of safety

The primary endpoints of safety are as follows:

- the occurrence of AEs
- the occurrence of drug related AEs
- the occurrence of SAEs

5.2.1.2 Secondary endpoints of safety

Not applicable as there are no secondary endpoints of safety.

5.2.1.3 Further endpoints of safety

Safety and tolerability will be assessed in a descriptive way based on:

- Changes in vital signs and physical examination
- Adverse events (AEs)
- The occurrence of Adverse events of special interest (AESIs)
- Discontinuation of therapy due to AEs, SAE
- Changes in safety laboratory analysis

Immunogenicity testing (ADA) will be performed at the visits specified in Flow Chart in order to detect the emergence of antibodies. Immunogenicity will be evaluated in terms of time to antibody emergence starting from the time of first exposure to BI 655066 in either 1311.2 or 1311.13.

5.2.2 Assessment of adverse events

5.2.2.1 Definitions of adverse events

Adverse event

An adverse event (AE) is defined as any untoward medical occurrence, including an exacerbation of a pre-existing condition, in a patient in a clinical investigation who received a

Proprietary confidential information.

© 2018 Boehringer Ingelheim International GmbH or one or more of its affiliated companies. All rights reserved.

This document may not - in full or in part - be passed on, reproduced, published or otherwise used without prior written permission.

pharmaceutical product. The event does not necessarily have to have a causal relationship with this treatment.

Serious adverse event

A serious adverse event (SAE) is defined as any AE which results in death, is immediately life-threatening, results in persistent or significant disability / incapacity, requires or prolongs patient hospitalisation, is a congenital anomaly / birth defect, or is to be deemed serious for any other reason if it is an important medical event when based upon appropriate medical judgement which may jeopardise the patient and may require medical or surgical intervention to prevent one of the other outcomes listed in the above definitions.

Intensity of adverse event

The intensity grading of AEs will be performed according to Rheumatology Common Toxicity Criteria (RCTC) Version 2.0 developed by Outcome Measures in Rheumatology (OMERACT) ([R13-3515](#)). Cf. [Appendix 10.7](#) and ISF for intensity/severity classification.

Causal relationship of adverse event

Medical judgment should be used to determine the relationship, considering all relevant factors, including pattern of reaction, temporal relationship, de-challenge or re-challenge, confounding factors such as concomitant medication, concomitant diseases and relevant history. Assessment of causal relationship should be recorded in the case report forms.

Yes: There is a reasonable causal relationship between the investigational product administered and the AE.

No: There is no reasonable causal relationship between the investigational product administered and the AE.

Worsening of the underlying disease or other pre-existing conditions

Worsening of the underlying disease or of other pre-existing conditions will be recorded as an (S)AE in the (e)CRF.

Changes in vital signs, ECG, physical examination, and laboratory test results

Changes in vital signs, ECG, physical examination and laboratory test results will be recorded as an (S)AE in the (e) CRF, if they are judged clinically relevant by the investigator.

Adverse Events of Special Interest (AESI)

The following are considered as Adverse events of Special Interest (AESI):

Hepatic injury defined by the following alterations of liver parameters (for patients with normal liver function at baseline): an elevation of AST and/or ALT ≥ 3 fold upper limit of normal (ULN) combined with an elevation of total bilirubin ≥ 2 fold ULN measured in the

Proprietary confidential information.

© 2018 Boehringer Ingelheim International GmbH or one or more of its affiliated companies. All rights reserved.

This document may not - in full or in part - be passed on, reproduced, published or otherwise used without prior written permission.

same blood draw sample.

Patients showing these lab abnormalities need to be followed up according to [section 10.6](#) of this clinical trial protocol and the “Drug induced liver injury (DILI) checklist” provided in ISF.

- Major adverse cardiovascular events (MACE).

Including, but not limited to the following preferred terms: Atherosclerosis, Coronary artery disease, Myocardial infarction, Angina Pectoris, Transient ischemic attack, Cerebrovascular accident (including Stroke), Cardiac failure congestive, Peripheral arterial occlusive disease.

ASEIs are to be reported in an expedited manner similar to Serious Adverse Events, even if they do not meet any of the seriousness criteria – for details please see section 5.2.2.2.

5.2.2.2 Adverse event and serious adverse event reporting

All adverse events, serious and non-serious, occurring during the course of the clinical trial (i.e., from signing the informed consent onwards through the Residual Effect Period (REP) /Extended follow-up period) will be collected, documented and reported to the sponsor by the investigator on the appropriate CRF(s) / eCRFs / SAE reporting forms. Reporting will be done according to the specific definitions and instructions detailed in the ‘Adverse Event Reporting’ section of the Investigator Site File.

Reporting of Adverse Events in Remote Data Capture system (RDC):

AEs that are ongoing at the end of the previous trial (1311.2) will have to be re-entered, and any adverse events that have started between the two trials (in the event that the 6 weeks time-window is used), will also be entered into the 1311.13 RDC system.

Reporting of Adverse Events on the SAE form:

Specific instructions for the SAE reporting process concerning SAE forms in previous and roll-over studies will be provided in the ISF.

The REP for BI 655066 is 12 weeks. Therefore, all events reported within 12 weeks of the last trial medication will be considered on treatment. All adverse events will be reported up until the last per protocol visit (Extended EOS visit), which is 84 (+7 days) days after the last dose of trial medication.

The investigator does not need to actively monitor patients for AEs once the clinical trial has ended. However, if the investigator becomes aware of an SAE(s) that occurred after the patient has completed the clinical trial (including any protocol required REP and / or follow-up), it should be reported by the investigator to the sponsor if considered relevant by the investigator.

For each adverse event, the investigator will provide the onset date, end date, intensity, treatment required, outcome, seriousness, and action taken with the investigational drug. The

Proprietary confidential information.

© 2018 Boehringer Ingelheim International GmbH or one or more of its affiliated companies. All rights reserved.

This document may not - in full or in part - be passed on, reproduced, published or otherwise used without prior written permission.

investigator will determine the relationship of the investigational drug to all AEs as defined in [Section 5.2.2.1](#).

The investigator must report the following events using paper process SAE form via telephone/fax immediately (within 24 hours) to the sponsor: SAEs and non-serious AEs relevant to the SAE(s), and AESIs.

Boehringer Ingelheim has set up a list of AEs which are defined to be always serious. In order to support the investigator with the identification of these “always serious adverse events”, if a non-serious AE is identified to be serious per Boehringer Ingelheim definition, a query will be raised. The investigator must verify the description and seriousness of the event. If the event description is correct, the item “serious” needs to be ticked and an SAE has to be reported in expedited fashion following the same procedure as above.

The list of these adverse events can be found via the RDC-system.

With receipt of any further information to these events, a follow-up SAE report has to be provided. SAEs and non-serious AEs must include a causal relationship assessment made by the investigator.

The SAE form is to be forwarded to the defined unique entry point identified for the BI OPU (country-specific contact details will be provided in the Investigator Site File) or by using the electronic submission process. This immediate report is required irrespective of whether the investigational product has been administered or not and irrespective of causal relationship. It also applies if new information to existing SAEs or AESIs becomes available.

Pregnancy

In rare cases, pregnancy might occur in clinical trials. Once a female subject has been enrolled into the clinical trial, after having taken study medication, the investigator must report immediately any drug exposure during pregnancy to the sponsor. Drug exposure during pregnancy has to be reported immediately (within 24 hours or next business day whichever is shorter) to the defined unique entry point for SAE forms of the respective BI OPU (country-specific contact details will be provided in the Investigator Site File). The outcome of the pregnancy associated with the drug exposure during pregnancy must be followed up. In the absence of an (S)AE, only the Pregnancy Monitoring Form for Clinical Trials and not the SAE form is to be completed. The ISF will contain the Pregnancy Monitoring Form for Clinical Trials (Part A and Part B).

5.2.3 Assessment of safety laboratory parameters

The laboratory parameters that will be determined are listed in [Tables 5.2.3: 1](#) and [5.2.3: 2](#) at the time points provided in [Flow Chart](#). The respective reference ranges will be provided in the ISF. The laboratory tests will be performed at a designated central laboratory, and if necessary by additional specialist laboratories.

Laboratory results of the patients will be available in real time to the respective investigator and to the clinical monitor of each country (central laboratory website), and selected

Proprietary confidential information.

© 2018 Boehringer Ingelheim International GmbH or one or more of its affiliated companies. All rights reserved.

This document may not - in full or in part - be passed on, reproduced, published or otherwise used without prior written permission.

abnormal laboratory alerts will be sent automatically to the sites and to the sponsor in real time. PK, PD and biomarker data will not be available to the investigators or local clinical monitors, but only to the Trial Team (sponsor) and to the DMC.

Clinically relevant laboratory values will be commented on in the eCRF. A clinically relevant value may be either in- or outside the reference range. Clinically relevant abnormal laboratory test results must be repeated using an unscheduled visit lab kit and must be repeated until normalisation or stabilisation or until an alternative explanation has been found. Clinically relevant abnormal laboratory values will be also graded for intensity by using RCTC Version 2.0 criteria.

The tests listed in Table 5.2.3: 1 constitute laboratory tests and hormones (assessed in female patients only) that will be done only at the initial roll-over visit and at Extended EOT or Extended EOS after approval of amendment # 5 and start of the rollover of patients to the M15-997 study from 01-May-2018, i.e. these tests are only required at EV1 for patients that are having EV1 as their first 1311.13 visit. The results will not be included into the report. Samples will be archived and run as clinically necessary.

Table 5.2.3: 1 Exclusionary Testing

Category	Test name
Tb screening	Interferon-gamma release assay (IGRA)
Serum pregnancy test (only female patients of childbearing potential)	Serum β -Human Chorionic Gonadotropin

Table 5.2.3: 2 Safety laboratory tests

Category	Test name
Haematology	Haematocrit (Hct) Haemoglobin (Hb) Red Blood Cell Count / Erythrocytes Reticulocyte Count White Blood Cells / Leucocytes Platelet Count / Thrombocytes HbA1c (Haemoglobin (glycated Hb of A1c subtype)) Roll-over and final visits only

Table 5.2.3: 2

Safety laboratory tests (cont'd)

Category	Test name
Diff Automatic	Neutrophils (relative and absolute count) Eosinophils (relative and absolute count) Basophils (relative and absolute count) Monocytes (relative and absolute count) Lymphocytes (relative and absolute count)
Diff Manual (if Diff Automatic is abnormal)	Neutrophils, Bands (Stabs) Neutrophils, Polymorphonuclear (PMN) Eosinophils Basophils Monocytes Lymphocytes
Coagulation	Partial Thromboplastin Time (=aPTT) Prothrombin Time (Quick and International normalised ratio (INR))
Enzymes	Aspartate Aminotransferase/ Glutamate-Oxaloacetate Transaminase (AST/GOT) Alanine transaminase(Glutamic Pyruvate Transaminase (ALT/GPT) Alkaline Phosphatase (AP/ALP) Creatine Kinase (CK) CK-MB if CK is elevated Lactic Dehydrogenase (LDH)
Substrates	Glucose Creatinine Blood urea nitrogen Bilirubin Total Bilirubin Direct Protein, Total C-Reactive Protein (CRP) Uric Acid Cholesterol, total High density lipoprotein (HDL) Cholesterol Calculated low density lipoprotein (LDL) Cholesterol Triglycerides
Electrolytes	Calcium Sodium Potassium

Proprietary confidential information.

© 2018 Boehringer Ingelheim International GmbH or one or more of its affiliated companies. All rights reserved.

This document may not - in full or in part - be passed on, reproduced, published or otherwise used without prior written permission.

Table 5.2.3: 2

Safety laboratory tests (cont'd)

Category	Test name
Urinalysis (Stix)	Urine Nitrite Urine Protein Urine Glucose Urine Ketone Urobilinogen Urine Bilirubin Urine RBC/Erythrocyte Urine WBC/Leukocytes Urine pH Urine albumin (microalbumin urine test) (roll-over visit only)
Urine-Sediment (microscopic examination) (if urine analysis abnormal)	Urine Sediment Bacteria Urine Cast in Sediment Urine Squamous Epith Cells Urine Sediment Crystals, Unspecified Urine Sediment red blood cell count (RBC)/Erythrocytes Urine Sediment white blood cell count (WBC)/Leucocytes

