2.3 BENEFIT - RISK ASSESSMENT

Results of the Phase I study with BI 655066 (study 1311.1) suggest that a single injection intravenously or subcutaneously (i.v. or s.c.) of BI 655066 is associated with substantial and durable improvements in the cutaneous manifestations of psoriasis. At doses of 0.25 mg/kg intravenously and above, all active dose groups showed improvement in mean PASI scores of at least 75% from baseline by week 12, which lasted at least until week 24. Similar improvements were observed in both of the active BI 655066 subcutaneous dose groups ([M14-0004](#)).

Patients rolling over in this OLE will have completed the single blind 1311.2 study where 75% of all patients will have received BI 655066 at different dose levels. Based on the preliminary data from study 1311.1 described in [Section 1.2](#), where good tolerability was

Proprietary confidential information.

© 2018 Boehringer Ingelheim International GmbH or one or more of its affiliated companies. All rights reserved.

This document may not - in full or in part - be passed on, reproduced, published or otherwise used without prior written permission.

shown, and no drug related serious adverse events (SAE), patients are likely to benefit from participation in this study.

Risks of participating in this study include risks related to the trial specific procedures such as blood sampling, subcutaneous injection of study medication. Blood sampling and subcutaneous injections can cause local bruising, inflammation, and pain.

As with any immune modulating agent, BI 655066 has the potential to impair immune function resulting in a risk of infection. This will be addressed by clinical monitoring for AEs during the treatment and follow up periods. Interferon gamma (IFN- γ) release assay to *M. tuberculosis* will be obtained at the initial roll-over visit, in order to exclude or discontinue documented untreated patients with active or latent tuberculosis infection (TB). All patients will be re-tested at the Extended end of treatment visit in order to assess long-term impact of BI 655066 on *M. tuberculosis* exposure. Patients having current signs or symptoms of infection or history of serious infection will not be included in the study.

The role of IL-23 in tumour immunity is not well established at this time, but an increased risk of cancer from an IL-23 antagonist, though considered small, cannot be excluded.

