3.3.3 Exclusion criteria

1. Patients who experienced any drug related Serious Adverse Event in the preceding trial
2. Patients who have developed guttate, erythrodermic or pustular psoriasis or drug-induced psoriasis (as diagnosed by the investigator), during the preceding trial 1311.2.
3. Evidence of current or previous clinically significant disease, medical condition other than psoriasis, or finding of the medical examination (including vital signs and (electrocardiography (ECG)), that in the opinion of the investigator, would compromise the safety of the patient or the quality of the data.
4. Known clinically important acute or chronic infections including hepatitis, HIV. In regards to Tuberculosis the following applies:
 - Signs or symptoms suggestive of current active or latent tuberculosis upon medical history, physical examination and/or a chest radiograph (both posterior-anterior and lateral views, taken within 3 months prior to the first administration of study drug and read by a qualified radiologist).
 - History of latent or active TB prior to screening, except for patients with documented completion of an adequate treatment regimen, at least 6 months prior to the first administration of study agent.
 - Positive QuantiFERON-TB Gold In-Tube test (IGRA) within 2 months prior to the roll-over visit (if available) (cf. [Section 3.3.4.1](#)), in which active tuberculosis has not been ruled out. This does not apply to patients with history of latent tuberculosis with documented completion of an adequate treatment regimen, at least 6 months prior to the first administration of study agent.
5. Patients who have developed malignancy, or suspicion of active malignant disease during the preceding trial 1311.2 (except treated cutaneous squamous cell or basal cell carcinoma or carcinoma in situ of the cervix that have been adequately treated).

6. Intake of restricted medications (cf. [Section 4.2.2.1](#)) or other drugs considered likely to interfere with the safe conduct of the study, as assessed by the investigator.
7. Alcohol or drug abuse within 3 months prior to the roll-over visit that would interfere with trial participation or any ongoing condition leading to a decreased compliance to study procedures in the opinion of the investigator.
8. Any clinically significant laboratory abnormalities based on the last available lab results received during the preceding trial (according to the investigator's medical assessment) (cf. [Section 6.2.2.1](#)).

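### Protocol 5.2.3 makes running the IGRA and serum beta-HCG samples conditional and keeps the results out of the report, in conflict with the IGRA withdrawal rule (3.3.4.1) and the re-test of all patients (2.3)

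*Protocol*

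**What the plan says.** Protocol section 5.2.3 opens by covering both laboratory tables: "The laboratory parameters that will be determined are listed in" Tables 5.2.3:1 and 5.2.3:2. It adds: "Laboratory results of the patients will be available in real time to the respective investigator". Of Table 5.2.3:1, which holds the IGRA and serum beta-HCG, it says these are tests "that will be done only at the initial roll-over visit and at Extended EOT or Extended EOS". The same paragraph then ends with two sentences: "The results will not be included into the report", and "Samples will be archived and run as clinically necessary".

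Other sections rely on an IGRA result:

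- Section 2.3 gives the purpose of the roll-over IGRA: "in order to exclude or discontinue documented untreated patients with active or latent tuberculosis infection". It then says: "All patients will be re-tested at the Extended end of treatment visit in order to assess long-term impact of BI 655066 on" tuberculosis exposure.
- Section 3.3.4.1 requires withdrawal of a patient whose roll-over IGRA is positive, and cites Table 5.2.3:1.
- Section 4.2.1 sends patients with a positive roll-over IGRA to follow-up under local guidelines.
- Exclusion criterion 4 in section 3.3.3 uses an IGRA taken "within 2 months prior to the roll-over visit (if available"), and cross-refers to 3.3.4.1.

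**The concern.** A sample that is stored and assayed only on clinical need does not give a result for every patient. A patient with latent tuberculosis and no symptoms gives little clinical reason to run the assay, yet section 2.3 names latent infection as something the test should detect. If a site or laboratory followed the last sentence of that paragraph literally, the 3.3.4.1 withdrawal rule, the 2.3 safeguard and the 4.2.1 follow-up could not operate for such a patient. At the end of treatment, a re-test of everyone would shrink to those with a clinical reason.

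Reporting is a separate problem. Section 2.3 justifies the re-test as a way to learn the drug's long-term effect. A result that section 5.2.3 keeps out of the report cannot serve that purpose.

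**Working it through.** No planned figure is at issue, so the check is a comparison of texts, followed by date arithmetic for the size.

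**1. Scope of the sentence.** It closes the paragraph on the Table 5.2.3:1 tests and comes just before that table, so its samples are those for the IGRA and serum beta-HCG. No text limits it to residual material or to one of the two tests. Flow Chart footnote 13, attached to the TB screening row, refers the site to section 5.2.3 for details.

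**2. Side by side.**

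| Place | Is a result needed for every patient due the test? |
|---|---|
| 5.2.3, opening and timing sentences | Yes |
| 5.2.3, last sentence of the Table 5.2.3:1 paragraph | No, only on clinical need |
| 2.3, roll-over IGRA and re-test | Yes; the re-test covers all patients |
| 3.3.4.1, withdrawal on a positive roll-over IGRA | Yes; the rule cannot act without one |
| 4.2.1, follow-up of positives | Presupposes testing, but does not itself require it |

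**3. Backstops.** Exclusion 4 uses a prior IGRA only where one exists. History, examination and the clinical withdrawal grounds in 3.3.4.1 remain, but they do not replace an IGRA in a patient without symptoms. For pregnancy the gap is small: Flow Chart footnote 16 requires a urine test before each dose in women of childbearing potential.

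**4. Reporting.** The SAP's laboratory list (section 11.3.1, Table 3) has no IGRA. The SAP's areas of safety interest (section 11.2.1, Table 2) include a tuberculosis query that covers investigations and feeds the adverse event overview. Under Protocol 5.2.2.1, a laboratory change becomes an adverse event only if the investigator judges it clinically relevant. A positive IGRA so recorded at Extended EOS would come at most 84 + 7 = 91 days after the last dose, inside the SAP's 105-day treatment-emergent window. The query can therefore show some positives. It cannot show how many patients were tested or how many were negative.

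**5. Size at roll-over.** Inputs: protocol version dated 30-Jan-2018; EV2 at day 84 and EV3 at day 168, each ±7 days; after 01-May-2018 and country approval, the next visit is the non-dosing Extended EOS (Flow Chart footnotes 8c and 23). Assume the earliest case, with approval and EV1 both on 30-Jan-2018 as day 1.

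- EV2: day 84 − 7 = 77 to 84 + 7 = 91, that is 16-Apr-2018 to 30-Apr-2018, before 01-May-2018.
- EV3: day 168 − 7 = 161 at the earliest, that is 09-Jul-2018, after 01-May-2018, so Extended EOS replaces it.
- Doses after EV1 in this trial: at most 1, and 0 for later entrants.

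The number of new entrants under this version is not given and may be zero.

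**6. Size at end of treatment.** Patients still in the trial are due the test at Extended EOT or Extended EOS. Their number is not given. With planned enrolment of about 100, the range is 0 to about 100.

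**The case against.** The strongest reply is that routine testing is plainly intended. Excluding results from the report presupposes that results exist. The same section says the tests are done, and the title of Table 5.2.3:1 calls them exclusionary. The Flow Chart schedules TB screening with no condition on symptoms, and amendment 5 added it to the Extended EOS visit because that becomes the last visit. The archive sentence could mean that sample left over is kept for further runs, and the Central Laboratory Manual, which is not among the documents, may say so. All of this stands as evidence of intent, and it is why the point is minor. It does not remove the conflict, because the text does not contain that limit.

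Three stronger readings are tempting and are not supported:

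- A reader might infer that IGRAs were left unassayed. Nothing in the documents shows this.
- A reader might infer that end-of-treatment positives can never reach the analysis. The SAP's tuberculosis query gives them a route if they are recorded as adverse events.
- A reader might infer that section 6.2.2.1 is deficient because its re-check list names inclusion 3 and exclusion 8 but not the IGRA, or that a rule to review results before the next dose is missing. That list concerns entry criteria judged on earlier laboratory results. The roll-over IGRA has its own standing rule in 3.3.4.1, so neither addition is needed.

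**Conclusion.** The conflict is real and minor. One sentence in 5.2.3, probably a slip, contradicts the rest of that section, the withdrawal rule in 3.3.4.1 and the re-test of all patients in 2.3. A second sentence, on reporting, defeats the purpose stated for the re-test, and the SAP makes up for this only in part.

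The practical weight lies with the end-of-treatment IGRA, where 0 to about 100 patients are due; the upper end is planned enrolment, not a current count. At roll-over the exposure under this version is at most one further dose per new entrant, possibly for no one. Patients who entered earlier had their roll-over visit under protocol text that is not available here, so nothing is claimed about them. The conclusion assumes that no laboratory document outside the protocol already restricts the archive sentence to residual sample.

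**What to change.** In 5.2.3, delete the archive sentence or limit it to residual sample left after the required assay. It should then be clear that the IGRA and serum beta-HCG are run for every patient due for them at roll-over and at Extended EOT or Extended EOS.

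For reporting, choose one of two routes. Either lift the reporting exclusion in 5.2.3 for the end-of-treatment IGRA and add one count (tested, positive) or a listing, or reword section 2.3 so that it no longer gives assessment of long-term impact as the purpose of the re-test.

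The cost is a few words, plus assays that the protocol already requires and, if that route is taken, one small output. No visit, blood draw or procedure is added. A protocol change does need ethics and authority approval under section 8.1, at approximately 24 sites in 4 countries, late in the trial. It would therefore sensibly travel with any other amendment.
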